9.1.1.2 Baseline Period

The purpose of the Baseline Period is to establish disease characteristics prior to starting treatment, and to confirm protocol eligibility as specified in the inclusion/exclusion criteria. Results of baseline assessments must be obtained and reviewed by the investigator prior to the first dose of study drug (C1D1) to confirm eligibility. Baseline assessments will be performed on Day -1 prior to treatment on C1D1.

Subjects who complete the Baseline Period and meet the criteria for inclusion/exclusion (Sections 9.3.1 and 9.3.2) will begin the Treatment Phase.

9.1.2 Treatment Phase

The Treatment Phase will begin at the time of lenvatinib administration on C1D1 and end following the last dose of lenvatinib. Subjects will be treated with lenvatinib dose of 24 mg (2 capsules of 10 mg each and 1 capsule of 4 mg) once daily by oral administration. Subjects will undergo safety and efficacy assessments. Subjects will discontinue treatment with lenvatinib at the time of disease progression (radiological or clinical), development of unacceptable toxicity (AE), lost to follow-up, withdrawal of consent, subject choice, pregnancy, or study termination by the sponsor.

9.1.3 Posttreatment Phase

The Posttreatment Phase will start at the End of Treatment visit and will continue as long as the subject is alive or until the study subject withdraws consent or is lost to follow-up. Subjects who discontinue study treatment before disease progression will continue to undergo tumor assessment every 6 weeks \pm 1 week for the first 24 weeks and every 8 weeks \pm 1 week thereafter, until documentation of disease progression or start of another anti-cancer therapy. Follow-up assessment for survival will be performed every 12 weeks \pm 1 week.

9.2 Discussion of Study Design, Including Choice of Control Groups

This multicenter, single arm, Phase 2 trial is designed to assess the efficacy and safety of lenvatinib in subjects with ATC, which is a rare aggressive disease with no established standard chemotherapy. Lenvatinib has established activity in RR-DTC and, more recently, an interim analysis of an ongoing Phase 2 study has also shown promising anti-tumor effects in a small cohort of ATC patients.

The current study is designed primarily to provide additional efficacy and safety data for single-agent lenvatinib in a larger cohort of ATC subjects. Efficacy endpoints (eg, ORR,

PFS, and OS) in lenvatinib-treated subjects will be compared to those from the historical controls based on published studies. The efficacy and safety parameters being evaluated are commonly used in oncology trials.

9.3 Selection of Study Population

Approximately 76 subjects will be enrolled at approximately 20 centers in the US, EU, and other regions, in collaboration with ITOG. Subjects who do not meet all of the inclusion criteria or who meet any of the exclusion criteria will not be eligible to receive study drug.

9.3.1 Inclusion Criteria

Subjects must meet all of the following criteria to be included in this study:

1. Males or females age ≥ 18 years at the time of ICF.
2. Subjects must have histological diagnosis consistent of ATC. Cytologic diagnosis by fine needle aspiration alone is not sufficient. Histologic diagnosis may be made by core needle biopsy, incisional biopsy, thyroidectomy, or other surgical biopsy. Fresh tumor biopsies (re-biopsy) should be obtained, whenever feasible. The central pathology review may take place prior to or after the subject starts treatment with lenvatinib.
 - a. Central review of pathology is required for study participation, but not required prior to enrollment or start of treatment in order to avoid delay. If the results of central pathology review are not available prior to the start of study treatment, the confirmation of diagnosis of ATC at the local laboratory is mandatory prior to scheduled start of treatment with lenvatinib.
 - b. If central pathology review indicates a diagnosis other than ATC, the subject may continue treatment with lenvatinib per standard of care, at the discretion of the treating investigator. Subjects deemed to have another diagnosis (not ATC) will be taken off this study and replaced for the purpose of efficacy analyses.
 - c. DTC with focus loci of ATC is allowed. If a subject has pathology showing a small focus of ATC arising out of DTC and the measurable disease is not fully consistent with ATC, confirmation of ATC by biopsy is required.
 - d. An incidental focus of MTC, DTC, and/or poorly differentiated thyroid cancer in a subject with ATC is allowed.
 - e. Histological diagnosis of ATC made through surgical resection is also acceptable.
3. Prior neoadjuvant, adjuvant or palliative chemotherapy for ATC is allowed.
4. Measurable disease based on investigator's assessments meeting the following criteria:
 - a. At least 1 lesion of ≥ 10 mm in the longest diameter for a non-lymph node or ≥ 15 mm in the short-axis diameter for a lymph node which is serially

- measurable according to RECIST 1.1 using computerized tomography (CT) or magnetic resonance imaging (MRI).
- b. Lesions that have had external beam radiotherapy or locoregional therapies such as radiofrequency ablation must show evidence of subsequent progressive disease (substantial size increase of $\geq 20\%$) to be deemed a target lesion.
5. Subjects with known brain metastases who have completed whole brain radiotherapy, stereotactic radiosurgery, or complete surgical resection will be eligible if they have remained clinically stable, asymptomatic, and off steroids for 1 month prior to enrollment.
 6. All previous chemotherapy or radiation therapy-related toxicities, except dry mouth, dysphagia, esophagitis, mucositis, alopecia, and irreversible late sequelae of radiation therapy, must have resolved to Grade 0 or 1 per Common Terminology Criteria for Adverse Events (CTCAE v 4.03), and all wounds from prior surgery must have adequately recovered.
 7. Eastern Cooperative Oncology Group (ECOG) performance status of 0 to 1.
 8. Blood pressure (BP) $\leq 140/90$ mmHg at screening with or without antihypertensive medications and no change in antihypertensive medications within 1 week prior to C1D1.
 9. Adequate renal function as evidenced by calculated creatinine clearance ≥ 30 mL/min according to the Cockcroft and Gault formula ([Appendix 4](#)).
 10. Adequate bone marrow function:
 - a. Absolute neutrophil count (ANC) $\geq 1.5 \times 10^9/L$ and
 - b. Hemoglobin ≥ 9.0 g/dL (can be corrected by growth factor or transfusion) and
 - c. Platelet count $\geq 100 \times 10^9/L$
 11. Adequate blood coagulation function as evidenced by an International Normalized Ratio (INR) ≤ 1.5
 12. Adequate liver function:
 - a. Bilirubin $\leq 1.5 \times$ upper limit of normal (ULN) except for unconjugated hyperbilirubinemia or Gilbert's syndrome
 - b. Alkaline phosphatase (ALP), alanine aminotransferase (ALT), and aspartate aminotransferase (AST) $\leq 3 \times$ ULN ($\leq 5 \times$ ULN if subject has liver metastases). If ALP is $> 3 \times$ ULN (in the absence of liver metastases) or $> 5 \times$ ULN (in the presence of liver metastases) AND subjects are also known to have bone metastases, the liver-specific ALP must be separated from the total and used to assess the liver function instead of the total ALP.
 13. Voluntary agreement to provide written ICF and the willingness and ability to comply with all aspects of the protocol.

9.3.2 Exclusion Criteria

Subjects who meet any of the following criteria will be excluded from this study:

1. DTC or MTC. However, ATC arising out of DTC is allowed, as long as the measurable disease is clinically consistent with ATC ie, rapidly progressive and/or ^{18}F fluorodeoxyglucose (FDG)-avid.
2. Newly diagnosed patients who are considered appropriate candidates for comprehensive multimodality treatment (involving surgery and/or external beam radiotherapy or chemo radiotherapy).
3. Prior treatment with lenvatinib or any tyrosine kinase inhibitor (except for combination therapy of radiation and reduced dose of TKI given for the purpose of radiosensitization).
4. Major surgery within 2 weeks prior to the first dose of lenvatinib.
5. Any anti-cancer treatment within 14 days or any investigational agent within 30 days before the first dose of study drug.
6. Radiotherapy within 3 weeks prior to the first dose of lenvatinib.
7. Subjects having $> 1+$ proteinuria on urine dipstick testing will undergo 24-hour urine collection for quantitative assessment of proteinuria. Subjects with urine protein ≥ 1 g/24 hours will be ineligible.
8. Significant cardiovascular impairment: History of (a) congestive heart failure greater than New York Heart Association (NYHA) Class II, (b) unstable angina, (c) myocardial infarction, (d) stroke, or (e) cardiac arrhythmia associated with impairment within 6 months of the first dose of study drug.
9. A clinically significant electrocardiogram (ECG) abnormality, including a marked baseline prolonged QT/QTc interval (eg, a repeated demonstration of a QTc interval >500 msec).
10. Active infection requiring systemic therapy.
11. Clinically significant hemoptysis or tumor bleeding within two weeks prior to first dose of lenvatinib.
12. Radiographic evidence of major blood vessel invasion/infiltration.
13. Other active malignancy (except definitively treated melanoma in-situ, basal or squamous cell carcinoma of the skin, or carcinoma in-situ of the cervix or bladder) within past 24 months.
14. Scheduled for major surgery during the study.
15. Females who are breastfeeding or pregnant at Screening or Baseline (as documented by a positive beta-human chorionic gonadotropin [β -hCG] (or human chorionic gonadotropin [hCG]) test with a minimum sensitivity of 25 IU/L or equivalent units of β -hCG [or hCG]). A separate baseline assessment is required if a negative screening pregnancy test was obtained more than 72 hours before the first dose of study drug.
16. Females of childbearing potential who:
 - Do not agree to use a highly effective method of contraception (ie, total abstinence [if it is their preferred and usual lifestyle], an intrauterine device or intrauterine system, a contraceptive implant, an oral contraceptive, or have a

vasectomized partner with confirmed azoospermia) within 30 days before study entry and throughout the entire study period and for 30 days after study drug discontinuation.

- Are currently totally abstinent (as their preferred and usual lifestyle), and do not agree to be totally abstinent during the study period and for 30 days after study drug discontinuation.
- Are using hormonal contraceptives but are not on a stable dose of the same hormonal contraceptive product for at least 4 weeks before dosing and who do not agree to use the same contraceptive during the study and for 30 days after study drug discontinuation.
- Are using oral hormonal contraceptives and who do not agree to add a barrier method.
- (NOTE: All females will be considered to be of childbearing potential unless they are postmenopausal [amenorrheic for at least 12 consecutive months, in the appropriate age group, and without other known or suspected cause] or have been sterilized surgically [ie, bilateral tubal ligation, total hysterectomy, or bilateral oophorectomy, all with surgery at least 1 month before dosing]).

For sites outside of the EU, it is permissible that if a highly effective method of contraception is not appropriate or acceptable to the subject, then the subject must agree to use a medically acceptable method of contraception, ie, double barrier methods of contraception such as condom plus diaphragm or cervical/vault cap with spermicide.

17. Evidence of clinically significant disease (eg, cardiovascular, respiratory, gastrointestinal, renal disease) that in the opinion of the investigator(s) could affect the subject's safety or interfere with the study assessments.
18. Known intolerance to the study drug or any of the excipients.
19. Any medical or other condition that in the opinion of the investigator(s) would preclude the subject's participation in a clinical study.

9.3.3 Removal of Subjects From Therapy or Assessment

The investigator may discontinue treating a subject with study treatment or withdraw the subject from the study at any time for safety or administrative reasons. The subject may decide to discontinue study treatment or withdraw from the study at any time for any reason. The reason for discontinuation will be documented. If a subject discontinues study treatment, the subject will enter the Follow-Up Period and complete protocol-specified off-treatment visits, procedures, and survival follow-up unless the subject withdraws consent. The investigator should confirm whether a subject will withdraw from study treatment but agree to continue protocol-specified, off-treatment study visits, procedures, and survival follow-up, or whether the subject will withdraw consent. If a subject withdraws consent, the date will be documented in the source documents. The Subject Disposition CRF page will be completed indicating the primary reason for discontinuation and all other reason(s)

contributing to the subject's discontinuation from treatment. In addition, the date of last dose of study drug will be recorded on the Study Drug Dosing CRF page.

During the Follow-Up Period, in subjects who have discontinued study treatment without documented disease progression (radiological or clinical), every effort should be made to continue monitoring their disease status by radiologic imaging every 6 weeks \pm 1 week for the first 24 weeks and every 8 weeks \pm 1 week thereafter from the date of the last assessment until (1) the start of new anticancer treatment, (2) disease progression (3) death, or (4) the end of the study, whichever occurs first.

All subjects will be followed for survival until death, except where a subject withdraws consent or the sponsor chooses to halt survival follow-up after completion of the primary study analysis.

9.4 Treatment

9.4.1 Treatment Administered

Subjects will take lenvatinib as described in [Table 1](#). Study subjects will be instructed to take study drug in the form of two 10-mg capsules and one 4-mg capsule containing lenvatinib (total of 3 capsules) with water each morning. Study drug is to be taken at approximately the same time each morning, with or without food.

Table 1 Treatment Administered

Drug Name	Strength	Oral Dose Form	Number Dispensed and Frequency
Lenvatinib	24 mg	Capsule	Two 10 mg capsules and one 4-mg capsule to be taken QD

QD = once a day

9.4.1.1 Criteria for Interruption of Treatment, Dose Reduction and Resumption of Treatment

Dose reduction and interruptions for subjects who experience toxicity will be made according to the guidelines provided in [Table 2](#).

Dose reductions will occur in succession based on the previous dose level (24, 20, 14, and 10 mg/day). Any dose reduction below 10 mg/day must be discussed with the sponsor. Once the dose has been reduced, it cannot be increased at a later date.

Table 2 Dose Reduction and Interruption Instructions for Lenvatinib-Related Toxicities

Treatment-Related Toxicity ^{a,b} including hepatic injury and thromboembolic events	Management	Dose Adjustment
Grade 1 and tolerable Grade 2		
	Continue treatment	No change
Intolerable Grade 2^c or Grade 3^{d,e}		
First occurrence	Interrupt until resolved to Grade 0-1 or baseline ^f	20 mg orally QD (one-level reduction)
Second occurrence (same toxicity or new toxicity)	Interrupt until resolved to Grade 0-1 or baseline ^f	14 mg orally QD (one-level reduction)
Third occurrence (same toxicity or new toxicity)	Interrupt until resolved to Grade 0-1 or baseline ^f	10 mg orally QD (one-level reduction)
Fourth occurrence (same toxicity or new toxicity)	Interrupt until resolved to Grade 0-1 or baseline ^f	Discuss with sponsor
Grade 4^g: Discontinue Study Treatment		

QD = once a day

Note: For grading, see Common Terminology Criteria for Adverse Events version 4.03. Collect all CTC grades of AEs, decreasing and increasing grade.

a: A delay of study treatment for more than 28 days (due to treatment-related toxicities) will require a discussion with the sponsor before treatment can be resumed.

b: Initiate optimal medical management for nausea, vomiting, and/or diarrhea prior to any study treatment, interruption, or dose reduction.

c: Grade 2 toxicities will be determined to be tolerable or intolerable by both the subject and investigator. If Grade 2 toxicity is determined to be intolerable, the dose of study drug will be reduced with or without dose interruption. Interruption for Grade 3 toxicities is mandatory.

d: Obese subjects with weight loss requiring dose interruption and reduction do not need to return to baseline or Grade 1 weight loss to restart lenvatinib. Based on the judgment of the investigator, subjects may be restarted at the lower dose of lenvatinib once the weight has been stable for at least 1 week. Normal BMI should be used as the new baseline for future dose reductions.

e: Not applicable to abnormal clinical laboratory values that are not clinically relevant based on the judgment of the investigator (eg, ALT, AST, γ -GTP values $< 10 \times$ ULN, and Na).

f: For hematology toxicities, restart treatment after toxicity resolves to Grade 2.

g: Excluding laboratory abnormalities judged to be non-life-threatening, in which case manage as Grade 3.

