7.1.2.2 Clinical Experience With Lenvatinib in Radioiodine-Refractory Differentiated Thyroid Cancer

In Phase 3 study E7080-G000-303 (Study 303) (Schlumberger et al, 2014), in subjects with RR-DTC, lenvatinib treatment demonstrated a statistically significant and clinically meaningful benefit as measured by PFS. Based on Independent Imaging Review assessments, lenvatinib prolonged median PFS by 14.7 months compared with placebo (18.3 months versus 3.6 months, respectively). The difference in PFS between the lenvatinib and placebo arms was highly statistically significant ($P<0.0001$) using both stratified and unstratified log-rank tests. The hazard ratio estimated from the stratified Cox proportional hazard model was 0.21 (99% confidence interval [CI]: 0.14, 0.31) in favor of lenvatinib.

Lenvatinib treatment also resulted in a highly statistically significant effect on response rate (complete response [CR] + partial response [PR]) compared with placebo (64.8% versus 1.5%; $P<0.001$). Four subjects in the lenvatinib arm had a CR, an atypical finding for an antiangiogenic agent. The objective response rate (ORR) of the lenvatinib-treated subjects at 6 months was 57.5% (n=150). Thus, at 6 months, approximately 89% of the subjects who ultimately responded had already achieved a response.

About 79% of subjects in Study 303 needed dose reductions from the starting dose of 24 mg because of treatment-emergent AEs (TEAEs), with the second and third most frequent doses administered being 14 mg and 20 mg, respectively. The most frequently reported TEAEs ($\geq 30\%$ of subjects, any grade) in the lenvatinib arm of the Safety Analysis Set were (in descending order of frequency) hypertension, fatigue, diarrhea, arthralgia/myalgia, decreased appetite, weight decreased, nausea, stomatitis, headache, vomiting, proteinuria, palmar-plantar erythrodysesthesia syndrome, abdominal pain, and dysphonia. Hypertension and proteinuria were the TEAEs that led to dose reductions most frequently.

In Study 303, PFS was significantly longer in lenvatinib-treated subjects who had a TEAE of hypertension during treatment compared with subjects who did not develop hypertension during treatment (18.8 versus 12.9 months, respectively; $P=0.0085$, unstratified log-rank test).

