9.4.1.1.1 MANAGEMENT OF HYPERTENSION

The following guidelines should be followed for the management of systolic BP ≥ 140 mmHg up to < 160 mmHg or diastolic BP ≥ 90 mmHg up to < 100 mmHg confirmed on repeat measurements after an hour:

- Continue lenvatinib and institute antihypertensive therapy for subjects not already receiving this.
- For those subjects already on antihypertensive medication, the dose of the current agent may be increased, if appropriate, or one or more agents of a different class of antihypertensive should be added.

The following guidelines should be followed for the management of systolic BP \geq 160 mmHg or diastolic BP \geq 100 mmHg confirmed on repeat measurements after an hour :

- If systolic BP \geq 160 mmHg or diastolic BP \geq 100 mmHg persists despite maximal antihypertensive therapy, then lenvatinib administration should be interrupted and restarted at a dose of 20 mg once daily (or one dose level reduction) when systolic BP \leq 150 mmHg and diastolic BP \leq 95 mmHg and the subject has been on a stable dose of antihypertensive medication for at least 48 hours.
 - If systolic BP \geq 160 mmHg or diastolic BP \geq 100 mmHg recurs on the 20-mg once daily dose despite optimal management of hypertension with antihypertensive medications (either by dose increase or the addition of a different class of antihypertensive), then lenvatinib administration should be interrupted and restarted at a dose of 14 mg once daily (one dose level reduction) only when systolic BP \leq 150 mmHg and diastolic BP \leq 95 mmHg and the subject has been on a stable dose of antihypertensive medication for at least 48 hours.
 - If systolic BP \geq 160 mmHg or diastolic BP \geq 100 mmHg recurs on the 14-mg once daily dose despite optimal management of hypertension with antihypertensive medications (either by dose increase or the addition of a different class of antihypertensive), then lenvatinib administration should be interrupted and restarted at a dose of 10 mg once daily (one dose level reduction) only when systolic BP \leq 150 mmHg and diastolic BP \leq 95 mmHg and the subject has been on a stable dose of antihypertensive medication for at least 48 hours.
 - Additional dose reduction should be discussed with the sponsor.

The following guidelines should be followed for the management of Grade 4 hypertension (life-threatening consequences):

- Institute appropriate medical management
- Discontinue lenvatinib

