Appendix 6 Common Terminology Criteria for Adverse Events (v4.03)

The National Cancer Institute's CTCAE v4.0 published 28 May 2009 (v4.03: June 14, 2010) provides descriptive terminology to be used for AE reporting in clinical trials. A brief definition is provided to clarify the meaning of each AE term. To increase the accuracy of AE reporting, all AE terms in CTCAE version 4.0 have been correlated with single-concept, MedDRA terms.

Grades in CTCAEs v4.03 refer to the severity of the AE. Grades of 1 through 5, with unique clinical descriptions of severity for each AE, are based on this general guideline:

Grade	CTCAE Status
1	Mild: asymptomatic or mild symptoms; clinical or diagnostic observations only; intervention not indicated.
2	Moderate: minimal, local, or noninvasive intervention indicated; limiting age-appropriate instrumental activities of daily living (ADL). ^a
3	Severe or medically significant but not immediately life-threatening: hospitalization or prolongation of hospitalization indicated; disabling, limiting self-care ADL. ^b
4	Life-threatening consequences: urgent intervention indicated.
5	Death related to adverse event.

CTCAE = Common Terminology Criteria for Adverse Events.

a: Instrumental ADL refers to preparing meals, shopping for groceries or clothes, using the telephone, managing money, etc.

b: Self-care ADL refers to bathing, dressing and undressing, feeding self, using the toilet, taking medications, and not bedridden.

Adapted from the Cancer Therapy Evaluation Program, NCI. CTCAE v4.0. Available from:

<http://evs.nci.nih.gov/ftp1/CTCAE/About.html> (Accessed 02 Oct 2014).

For further details regarding MedDRA, refer to the MedDRA website at: <http://www.meddrasso.com>. CTCAE v4.0 is available online at: <http://evs.nci.nih.gov/ftp1/CTCAE/About.html> (Accessed 02 Oct 2014).

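### Table 2 and the hypertension section give different triggers for interrupting lenvatinib and different restart tests, no text says which prevails, and the 160/100 mmHg tier leaves one situation without an instruction

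*Protocol*

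**What the plan says.** Protocol Section 9.4.1.1 opens with a general rule: "Dose reduction and interruptions for subjects who experience toxicity will be made according to the guidelines provided in" Table 2. For intolerable Grade 2 or Grade 3 toxicity, the table's management entry is "Interrupt until resolved to Grade 0-1 or baseline", followed by a one-level reduction. Footnote c adds: "Interruption for Grade 3 toxicities is mandatory". A reduced dose may not be raised again.

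The table's footnotes make exceptions:
- Footnote d gives obese subjects with weight loss their own restart rule.
- Footnote e reads: "Not applicable to abnormal clinical laboratory values that are not clinically relevant based on the judgment of the investigator".
- Footnote f reads: "For hematology toxicities, restart treatment after toxicity resolves to Grade 2".
- Footnote g moves certain Grade 4 laboratory findings to Grade 3 handling.

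None mentions hypertension.

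Section 9.4.1.1.1 then manages hypertension by pressure tier. If systolic pressure of at least 160 mmHg or diastolic of at least 100 mmHg "persists despite maximal antihypertensive therapy, then lenvatinib administration should be interrupted and restarted at a dose of 20 mg once daily" (or one level down), restart requires systolic of at most 150 and diastolic of at most 95, with at least 48 hours on a stable antihypertensive dose. Recurrence on 20 mg or 14 mg despite optimal management leads to a further interruption and step down. The synopsis carries both texts, as its Table 1 and its hypertension paragraph.

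**The concern.** Two passages address the same event and differ on when to stop and when to restart. One site could interrupt at a first confirmed high reading and reduce the dose permanently. Another could keep dosing and add antihypertensives. Each could cite the protocol.

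The event is not rare in the sponsor's own experience. Section 7.1.2.2 says of Study 303: "Hypertension and proteinuria were the TEAEs that led to dose reductions most frequently". Section 7.2 names hypertension as the most frequent treatment-related event in the Japanese Phase 2 study, which included 11 ATC subjects.

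Patient safety comes first. Beyond that, safety and tolerability is a secondary objective. SAP Sections 5.6.1 and 5.6.2 report reductions, interruptions, time to first reduction, dose intensity and adverse events leading to dose changes, and SAP Section 5.2.3 reports major deviations. Each of these can depend on which passage a site followed.

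**Working it through.** No sample size, power or error rate is involved. The check sets the passages side by side and compares the thresholds.

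| Question | Section 9.4.1.1, Table 2 | Section 9.4.1.1.1 |
|---|---|---|
| When to interrupt | Grade 3: always, apart from footnoted exceptions | At or above 160 systolic or 100 diastolic, only if it persists despite maximal therapy or recurs at a reduced dose despite optimal management |
| When to restart | Grade 0-1 or baseline | At or below 150 systolic and 95 diastolic, with at least 48 hours on stable medication |
| Dose after restart | One level down | One level down |
| Link to the other text | Hypertension not excepted | No reference to Table 2 |

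**Step 1: trigger.** Table 2 works by CTCAE grade, Section 9.4.1.1.1 by mmHg. To compare them, 160/100 mmHg or more must be given a grade. The hypertension section names its next tier Grade 4, which supports Grade 3 for the tier below. The protocol does not print hypertension-specific grades; Appendix 6 gives only general definitions. On the assumption of Grade 3, take a subject on 24 mg, on no antihypertensive, with a first confirmed 165/102. Table 2 interrupts and resumes at 20 mg. Under Section 9.4.1.1.1 the condition for interruption is not met.

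**Step 2: the gap.** This step needs no grading assumption. The instruction to continue lenvatinib and start antihypertensives belongs to the tier from 140 to below 160 systolic or 90 to below 100 diastolic. The tier above begins its instructions at failure of maximal therapy. For the 165/102 subject it states no action, so continuing is an inference. Table 4 footnote l requires two-weekly pressure monitoring at this level but says nothing about dosing.

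**Step 3: restart.** The screening limit is 140/90 (Section 9.3.1, criterion 8).
- Ceiling against screening limit: 150 − 140 = 10 mmHg systolic; 95 − 90 = 5 mmHg diastolic.
- Values of 141 to 150 systolic or 91 to 95 diastolic fall inside the lower tier, where the same section calls for antihypertensive therapy.
- Appendix 6 describes Grade 1 as "Mild: asymptomatic or mild symptoms; clinical or diagnostic observations only; intervention not indicated".

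A held subject at 148/94, on a stable antihypertensive dose for at least 48 hours, may therefore restart under Section 9.4.1.1.1 but is not clearly at Grade 0-1 under Table 2. Whether such a subject is back at baseline depends on the individual.

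**Step 4: precedence.** Sections 9.4.1.1.2 to 9.4.1.1.5 (proteinuria, hepatotoxicity, thromboembolic events, PRES) each send the reader back to the dose-reduction instructions. The hypertension section does not, and no sentence anywhere ranks it above or below Table 2.

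**The case against.** The best defence is that a specific rule displaces a general one. Section 9.4.1.1.1 is a subsection with its own tiers, trigger, restart test, dose steps and Grade 4 instruction. The missing link to Table 2 may mean it was written to stand alone, and the table's header names hepatic injury and thromboembolic events but not hypertension. This reading is plausible, but the protocol does not state it. Other exceptions to the table are footnoted, and footnote c is phrased as mandatory. Even if the reading is accepted, the gap in Step 2 remains.

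Four narrower objections stand and limit the point:
- Grade 3 for 160/100 mmHg is an assumption. The general Grade 3 wording in Appendix 6 would not by itself settle it.
- The 140/90 limit applies at screening. Vital signs are taken again at the Baseline visit, and SAP Section 8 takes the last value before first dose as baseline. Some subjects, including some treated at entry, might meet Table 2's baseline alternative at a value above 140/90.
- Both passages use the 24, 20, 14 and 10 mg sequence, so the dose steps themselves do not conflict.
- That sites would act differently is a possibility; the documents do not show it happening.

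**Conclusion.** The two passages need reconciling. The absence of any precedence statement and the missing instruction at 160/100 mmHg are plain from the text. The trigger conflict holds if 160/100 mmHg is Grade 3. The restart tests differ in wording for any hypertension event that Table 2 covers; in practice they may coincide for subjects whose baseline qualifies.

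A reader might infer more than the documents support:
- That Table 2 requires interruption for Grade 3 without exception. Footnote e exempts some laboratory values, and footnotes d and f vary the restart.
- That Section 9.4.1.1.1 tells sites to keep dosing at 160/100 until maximal therapy fails. It does not say so.
- That hypertension is the commonest cause of dose change here. Study 303 names it jointly with proteinuria, in radioiodine-refractory differentiated disease, and no ATC figure is given. The roughly 79% needing reductions in that study covers all adverse events.
- That the primary result is at risk. The exact binomial test of ORR, its population and its sample size do not depend on this text.

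The consequences are for patient safety, irreversible dose reductions, descriptive exposure summaries and deviation classification.

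**What to change.** Reconcile Table 2 with Section 9.4.1.1.1, and the two matching synopsis texts. Either a hypertension footnote in Table 2 or a cross-reference in Section 9.4.1.1.1 would do, provided that it states which passage governs interruption and which governs restart. Complete the 160/100 mmHg tier so that it states the action for a confirmed reading in a subject on no, or less than maximal, antihypertensive therapy. The sponsor chooses the clinical rule; this point takes no view on it.

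The cost is wording in an amendment and a letter to sites, with no added procedures or subjects. If dosing is already complete, record which passage was used to classify deviations, so that the exposure and deviation tables can be read correctly.
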